8.5.3. Efficacy Analyses for All GS-9883/F/TAF Analysis

The following analyses will be conducted for all GS-9883/F/TAF analysis using all GS-9883/F/TAF analysis set: (1) the proportion of subjects with HIV-1 RNA < 50 copies/mL by Missing = Excluded and Missing = Failure approaches by visit, (2) the change from baseline in CD4+ Cell Count by visits, and (3) the change from baseline in CD4 % by visits. No statistical comparison will be conducted for all GS-9883/F/TAF analysis.

8.6. Safety Analysis

All safety analyses will be performed using the safety analysis set for the double-blinded phase analysis and using all GS-9883/F/TAF analysis set for the all GS-9883/F/TAF analysis, unless specified otherwise.

All safety data collected on or after the date that the study drug was first administered up to the date of the last dose of study drug plus 30 days, unless specified otherwise, will be summarized for subjects in the safety analysis set according to the study drug received.

Data for the pretreatment period and the period post the date of last dose of study drug plus 30 days will be included in data listings for all enrolled subjects.

8.6.1. Extent of Exposure

A subject's extent of exposure to study drug will be generated from the study drug administration page in eCRF. Exposure data will be summarized by treatment.

Duration of exposure to study drug will be expressed as the number of weeks between the first and last dose of the study drug, inclusive, regardless of temporary interruptions in study drug administration and summarized by treatment.

Dosing information for individual subjects will be listed.

8.6.2. Adverse Events

Clinical and laboratory adverse events will be coded using the Medical Dictionary for Regulatory Activities (MedDRA). System Organ Class (SOC), High-Level Group Term (HLGT), High-Level Term (HLT), Preferred Term (PT), and Lower-Level Term (LLT) will be attached to the clinical database.

Events will be summarized on the basis of the date of onset for the event. A treatment-emergent adverse event will be defined as any adverse event with onset date on or after the study drug start date and no later than 30 days after the study drug stop date; or any adverse event leading to study drug discontinuation.

Summaries (number and percentage of subjects) of treatment-emergent adverse events (by SOC, HLT [if applicable], and PT) will be provided by treatment. Additional summaries will include summaries for adverse events by grade, Investigator's assessment of relationship to study drug, and effect on study drug dosing.

On an ongoing basis adverse events will be reviewed for events that might meet the definition of Stage 3 Opportunistic Illnesses in HIV are indicative of an AIDS-Defining Diagnoses. The Gilead medical personnel will review the possible Stage 3 events and approve the events that meet the definition. Those events that do meet the Stage 3 Opportunistic Illness definition of an AIDS-Defining Diagnosis will be listed.

A listing of Stage 3 Opportunistic Illnesses in HIV, can be found in [Appendix 6](#).

8.6.3. Laboratory Evaluations

Selected laboratory data (using conventional units) will be summarized using only observed data. Absolute values and changes from baseline at all scheduled visits will be summarized.

Graded laboratory abnormalities will be defined using the grading scheme defined in Grading of laboratory abnormalities attached in [Appendix 5](#).

Incidence of treatment-emergent laboratory abnormalities, defined as values that increase at least 1 toxicity grade from baseline at any time post baseline up to and including the date of last dose of study drug plus 30 days, will be summarized by treatment. If baseline data are missing, then any graded abnormality (i.e., at least a Grade 1) will be considered treatment emergent. The maximum post baseline toxicity grade will be summarized by laboratory parameter.

Laboratory abnormalities that occur before the first dose of study drug or after the last dose of study drug plus 30 days will be included in a data listing.

8.6.4. Other Safety Evaluations

Vital signs and safety ECG data will be summarized as appropriate.

8.7. Pharmacokinetic Analysis

CCI

For the general PK analyses, the pharmacokinetics of GS-9883 may be evaluated using descriptive statistics or population approaches.

TAF and FTC concentrations may be analyzed and PK parameters summarized as applicable.

8.8. Patient Reported Outcomes (PRO)

The PRO measures based on questionnaires (e.g. SF-36 and HIV Symptoms Distress Module) may be summarized using descriptive statistics.

8.9. Sample Size

A total of approximately 600 HIV-1 infected subjects, randomized in a 1:1 ratio to 2 treatment groups (300 subjects per treatment group), achieves at least 95% power to detect a non-inferiority margin of 12% in Week 48 response rate (HIV-1 RNA < 50 copies/mL as defined by the US FDA-defined snapshot algorithm) difference between the 2 treatment groups. For the sample size and power computations, it is assumed that both treatment groups have a response rate of 91% (based on Gilead Studies GS-US-292-0104 and GS-US-292-0111), that the non-inferiority margin is 12%, and that the significance level of the test is at a one-sided 0.025 level. Sample size and power calculations were made using the statistical software package nQuery Advisor (Version 6.0).

8.10. Data Monitoring Committee

An external Independent Data Monitoring Committee (IDMC) will review the progress, efficacy, and safety data of this study while the study is ongoing. The committee will convene after approximately the first 50% of subjects enrolled complete Week 12 visit or prematurely discontinue from the study drug, as well as after all subjects have completed their Week 24 visit or prematurely discontinued from the study drug. However, Gilead will defer to the IDMC for any decision to convene earlier or more frequently. The IDMC will examine the safety results of the trial and also focus on logistical issues such as accrual, retention, quality of clinical and laboratory data, and implications of results of external studies. Blinding will be preserved during the conduct of the study and access to unblinded data will be limited to designated parties.

No formal stopping rules will be used by the IDMC for safety outcomes. Rather, a clinical assessment will be made to determine if the nature, frequency, and severity of adverse events associated with a study regimen warrant the early termination of the study in the best interest of the participants.

For each IDMC analysis performed prior to the analysis of the primary efficacy endpoint, an alpha penalty of 0.00001 will be applied for the primary analysis of the primary endpoint.

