- The proportion of subjects who achieve HIV-1 RNA < 20 copies/mL at Weeks 48, 96, and 144 as defined by the US FDA-defined snapshot algorithm
- The change from baseline in log₁₀ HIV-1 RNA and in CD4+ cell count at Weeks 48, 96, and 144
- The proportion of subjects who achieve HIV-1 RNA < 50 copies/mL at Weeks 48 OL and 96 OL as defined by Missing = Excluded and Missing = Failure algorithm
- The change from baseline in CD4+ cell count at Weeks 48 OL and 96 OL.

Pharmacokinetics:

CCI [REDACTED]

For all subjects on study drug, a single anytime pre or post-dose PK blood sample will be collected at Weeks 8, 24, and 36.

For all subjects on study drug, a trough PK blood sample will be obtained 20-28 hours following the last dose at Weeks 4 and 12. Following an observed dose, one post-dose PK blood sample will be collected between 1 and 4 hours post-dose.

CCI [REDACTED]

The concentration of GS-9883 may be summarized using descriptive statistics. The pharmacokinetics of GS-9883 may be evaluated using population approaches. TAF and FTC concentrations may be analyzed and PK may be summarized as applicable.

CCI [REDACTED]

[REDACTED]

CCI [REDACTED]

[REDACTED]

Patient Reported Outcomes:

Short Form 36 Health Survey (SF-36), HIV Symptoms Distress Module, Work Productivity and Activity Impairment Questionnaire (WPAI) and Pittsburgh Sleep Quality Index (PSQI) will be administered at Day 1, Weeks 4, 12 and 48.

Statistical Methods:

The primary analysis will consist of a non-inferiority test of GS-9883/F/TAF versus DTG + F/TAF, with respect to the proportion of subjects who achieve HIV-1 RNA < 50 copies/mL at Week 48 as defined by the US FDA-defined snapshot algorithm.

It will be concluded that GS-9883/F/TAF is non-inferior to DTG + F/TAF if the lower bound of the 2-sided 95% confidence interval (CI) of the difference (GS-9883/F/TAF – DTG + F/TAF) in the response rate (HIV-1 RNA < 50 copies/mL as defined by the

US FDA-defined snapshot algorithm) is greater than -12%; i.e., a margin of 12% is applied to non-inferiority assessment. The 95% CI will be constructed using a normal approximation method based on stratified Mantel-Haenszel proportions, where stratification factors include baseline HIV-1 RNA level ($\leq 100,000$ copies/mL, vs. $> 100,000$ copies/mL) and region (US vs. Ex-US).

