8.5.1.3. Analysis of Primary Efficacy Endpoint

The null hypothesis is that the proportion of subjects achieving HIV-1 RNA < 50 copies/mL (as defined by the US FDA-defined snapshot algorithm) at Week 48 in GS-9883/F/TAF is at least 12% lower than the response rate in DTG + F/TAF; the alternative hypothesis is that the response rate in GS-9883/F/TAF is less than 12% lower than that in DTG + F/TAF.

Non-inferiority will be assessed using the conventional confidence interval approach. The point estimate of treatment difference (GS-9883/F/TAF group – DTG + F/TAF group) and the associated 2-sided 95% confidence interval will be constructed using a normal approximation method based on stratum-stratified Mantel-Haenszel proportions, where stratification factors include baseline HIV-1 RNA level ($\leq 100,000$ copies/mL, vs. $> 100,000$ copies/mL) and region (US vs. Ex-US). Note that to avoid small or missing cells in analysis strata, CD4+ cell count is not stratified in the analysis because HIV-1 RNA and CD4+ cell count are highly correlated.

If non-inferiority of GS-9883/F/TAF to DTG + F/TAF is established, the lower bound of the 95% CI will be compared to 0; if the lower bound of the 95% CI is greater than 0, then superiority of GS-9883/F/TAF over DTG + F/TAF will be established.

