2. TYPE OF PLANNED ANALYSIS

2.1. Data Monitoring Committee Analyses

The Week 12 Independent Data Monitoring Committee (IDMC) analysis was conducted after approximately the first 50% of subjects enrolled completed their Week 12 visit or prematurely discontinued the study drug. The Week 24 IDMC analysis was conducted after all subjects enrolled completed their Week 24 visit or prematurely discontinued the study drug. The purpose of these interim analyses was to provide the IDMC with a statistical report for review. More details are documented in the IDMC charter.

Gilead does not have a prior intent to ask the IDMC to review Week 48 results or to consider early termination of the study even if there is early evidence of favorable efficacy for B/F/TAF.

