Note that all data for subjects who actually receive DTG+F/TAF in the randomized phase and do not receive any dose of B/F/TAF in the extension phase will be excluded from all B/F/TAF analysis. The actual treatment received will differ from the randomized treatment only when the actual treatment received differs from randomized treatment for the entire treatment duration.

Analysis results will be presented using descriptive statistics. For categorical variables, the number and percentage of subjects in each category will be presented; for continuous variables, the number of subjects (n), mean, standard deviation (SD) or standard error (SE), median, first quartile (Q1), third quartile (Q3), minimum, and maximum will be presented.

All statistical tests will be 2-sided and performed at the 5% significance level unless otherwise specified.

For All B/F/TAF analysis, no statistical comparison between treatment groups will be conducted.

By-subject listings will be presented for all subjects in the All Randomized Analysis Set unless otherwise specified, and sorted by subject ID number, visit date, and time (if applicable). Data collected on log forms, such as AEs, will be presented in chronological order within a subject. The treatment group to which subjects were randomized will be used in the listings. Most listings will be provided for all randomized analysis set for data from both phases of the study. Some listings for All B/F/TAF analysis set will also be provided.

In general, age (in years) on the date of the first dose of study drug will be used for analyses and presentation in listings. For randomized but never dosed subjects, age on the date of randomization will be used. For screen failures, age on the date of the informed consent was signed will be used. If only birth year is collected on the eCRF, “01 January” will be used for the unknown birth day and month for the purpose of age calculation, similarly, if only birth year and month are collected on the eCRF, “01” will be used for the unknown birth day for the purpose of age calculation.

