3.5. Multiple Comparisons

No alpha level adjustment is applied other than for the primary endpoint.

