6.1. Primary Efficacy Endpoint

The primary efficacy endpoint is the proportion of subjects with HIV-1 RNA < 50 copies/mL at Week 48 as determined by the US FDA-defined snapshot algorithm {[U. S. Department of Health and Human Services 2015](#)}. The proportions are expressed as percentages for presentation purposes.

The statistical analysis methods for the primary efficacy endpoint were described in the Week 48 SAP and the analysis was performed in the Week 48 analysis.

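### Should the primary decision rules print a confidence level adjusted for the IDMC alpha penalty in Protocol 8.10?

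*Protocol*

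**What the plan says.** Protocol 8.10 plans two IDMC reviews, one when about half the subjects have reached Week 12 and one when all have reached Week 24, and lets the committee meet sooner or more often. For each IDMC analysis that precedes the primary analysis, "an alpha penalty of 0.00001 will be applied for the primary analysis of the primary endpoint".

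The decision rules are printed elsewhere:

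- The synopsis concludes non-inferiority "if the lower bound of the 2-sided 95% confidence interval (CI) of the difference" lies above -12%. It has no superiority rule.
- Protocol 8.5.1.3 builds the same two-sided 95% interval for non-inferiority and then adds that "if the lower bound of the 95% CI is greater than 0, then superiority of GS-9883/F/TAF over DTG + F/TAF will be established".
- Protocol 8.9 states, as a power input, that "the significance level of the test is at a one-sided 0.025 level".

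The SAP supplied is the one for the final analysis. Section 2.1 describes both IDMC analyses as done; for the second, "The Week 24 IDMC analysis was conducted after all subjects enrolled completed their Week 24 visit" or stopped study drug early. Section 3 sets a general default: "All statistical tests will be 2-sided and performed at the 5% significance level unless otherwise specified". Section 3.5 says: "No alpha level adjustment is applied other than for the primary endpoint". Section 6.1 places the primary methods in another document: "The statistical analysis methods for the primary efficacy endpoint were described in the Week 48 SAP".

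**The concern.** Taken literally, 8.10 means that the primary interval cannot be exactly 95% once any IDMC analysis has taken place, and two had. Yet both places that print the non-inferiority rule, and the one that prints the superiority rule, use an unadjusted 95% and do not point to 8.10. Someone working from the synopsis or 8.5.1.3 alone would apply a level that departs from the protocol's own error-control rule.

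The second difficulty is that 8.10 does not name the alpha being reduced. Protocol 8.9 speaks of one-sided 0.025 and SAP section 3 of two-sided 5%. Taking 0.00001 per look off one or the other gives different adjusted levels. The interval carries both confirmatory decisions, so a pre-specified rule ought to lead to a single threshold.

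**Working it through.** **Inputs.** Response 91% in both arms, 300 per arm, margin 12 points, one-sided alpha 0.025 (Protocol 8.9). Penalty 0.00001 per look (Protocol 8.10). Number of looks k = 2 (SAP 2.1). The variance is the simple unstratified, unpooled one; the planned analysis uses stratified Mantel-Haenszel proportions, so the figures indicate size rather than reproduce the analysis.

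**The plan's own figure first.**

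- SE = sqrt(2 × 0.91 × 0.09 / 300) = 0.0233666.
- Power = Φ(0.12 / 0.0233666 − 1.959964) = Φ(3.1756) = 0.99925.

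The protocol claims at least 95%. That is true as a lower bound: by the same formula 148 per arm already give 95%.

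**Penalty applied under each reading.**

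- Off the two-sided alpha: 0.05 − 2 × 0.00001 = 0.04998, a 95.002% interval.
- Off the one-sided alpha: 0.025 − 2 × 0.00001 = 0.02498, or 0.04996 two-sided, a 95.004% interval.

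Half-width = z × SE:

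| Case | CI level | z | Half-width (points) | Shift of bound (points) | Power |
|---|---|---|---|---|---|
| No penalty | 95% | 1.959964 | 4.5798 | – | 0.99925 |
| k = 2, two-sided reading | 95.002% | 1.960135 | 4.5802 | 0.0004 | 0.99925 |
| k = 2, one-sided reading | 95.004% | 1.960306 | 4.5806 | 0.0008 | 0.99925 |

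The sample size per arm for 95% power is 148 in all three rows. To two decimals both adjusted levels print as 95.00%.

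**More looks.** The documents record two. If there had been five (an assumption, used only to bound the effect), the level would be 95.005% or 95.010% and the shift 0.0010 or 0.0020 points.

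**Scale.** One subject changing outcome in an arm of 300 moves the crude difference by 1/300 = 0.333 points. That is about 830 times the shift under the two-sided reading (0.333 / 0.0004) and about 420 times the shift under the one-sided reading (0.333 / 0.0008).

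**Error rate if the penalty were ignored.** Adding back what 8.10 deducts for two looks gives a two-sided total of 0.05002 or 0.05004 instead of 0.05. Protocol 8.10 describes no efficacy boundary, and SAP 2.1 says the sponsor had no prior intent to ask the IDMC to consider stopping early for favourable efficacy. The penalty is therefore a token charge for looking at the data.

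**The case for a change.** The best case for a change is that pre-specification should produce one number. Reading 8.10 together with 8.5.1.3 settles that a penalty applies, but not which of two levels results. The SAP supplied does not help: section 3.5 implies an adjustment without giving a figure, and section 6.1 points to a document that is not here. A cross-reference and one adjusted level would cost almost nothing.

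Part of this stands. The supplied text does not name the side, and a cross-reference would have been tidier. Four things limit it.

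- The two alphas describe the same test. One-sided 0.025 and two-sided 0.05 coincide for this rule, and 8.9 uses the former only for the power calculation. Both printed rules are based on a two-sided interval, which makes two-sided 0.05 the natural reference. The choice is worth 0.0004 points.
- A final level could not have been printed in advance, because 8.10 leaves the number of IDMC meetings open. A charge per look is the sensible form, and the exact level belongs in the plan for the primary analysis.
- Non-inferiority and superiority are already read from the same interval in 8.5.1.3, so nothing needs aligning between the comparisons with -12% and 0.
- By the date of this SAP the Week 48 analysis was complete (SAP 2.2.1 and section 6). Writing k into the protocol afterwards would be record-keeping, not pre-specification.

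**Conclusion.** No change follows. This is a missing cross-reference and an unstated side for a penalty whose size, trigger and target are all in 8.10; no figure in the documents is miscalculated. An analyst who reads the protocol as a whole applies the penalty and reaches a sound conclusion under either reading. For two looks the bound moves by less than 0.001 percentage points, with power and sample size untouched. It could alter a decision only if the lower limit fell within about 0.001 points of -12% or of 0.

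This rests on the design assumptions of 91% response and 300 per arm, on an unstratified approximation to the planned interval, and on two IDMC analyses as reported in SAP 2.1. Whether the Week 48 SAP states the adjusted level cannot be checked here. SAP 3.5 suggests that an adjustment was planned, and the documents give no ground for saying that it was omitted.

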8.11. Analysis Schedule

The Week 48 OL analyses will be conducted after all subjects either complete their Week 48 OL visits or prematurely discontinue from the study drug. Final analysis and/or Week 96 OL analyses will be performed after all subjects complete the study or prematurely discontinue from the study.

9. RESPONSIBILITIES

9.1. Investigator Responsibilities

9.1.1. Good Clinical Practice

The investigator will ensure that this study is conducted in accordance with the principles of the Declaration of Helsinki (as amended in Edinburgh, Tokyo, Venice, Hong Kong, and South Africa), International Conference on Harmonisation (ICH) guidelines, or with the laws and regulations of the country in which the research is conducted, whichever affords the greater protection to the study subject. These standards are consistent with the European Union Clinical Trials Directive 2001/20/EC and Good Clinical Practice Directive 2005/28/EC.

The investigator will ensure adherence to the basic principles of Good Clinical Practice, as outlined in 21 CFR 312, subpart D, "Responsibilities of Sponsors and Investigators," 21 CFR, part 50, 1998, and 21 CFR, part 56, 1998.

The investigator and all applicable subinvestigators will comply with 21 CFR, Part 54, 1998, providing documentation of their financial interest or arrangements with Gilead, or proprietary interests in the investigational drug under study. This documentation must be provided prior to the investigator's (and any subinvestigator's) participation in the study. The investigator and subinvestigator agree to notify Gilead of any change in reportable interests during the study and for 1 year following completion of the study. Study completion is defined as the date when the last subject completes the protocol-defined activities.

9.1.2. Institutional Review Board (IRB)/Independent Ethics Committee (IEC) Review and Approval

The investigator (or sponsor as appropriate according to local regulations) will submit this protocol, informed consent form, and any accompanying material to be provided to the subject (such as advertisements, subject information sheets, or descriptions of the study used to obtain informed consent) to an IRB/IEC. The investigator will not begin any study subject activities until approval from the IRB/IEC has been documented and provided as a letter to the investigator.

Before implementation, the investigator will submit to and receive documented approval from the IRB/IEC any modifications made to the protocol or any accompanying material to be provided to the subject after initial IRB/IEC approval, with the exception of those necessary to reduce immediate risk to study subjects.

9.1.3. Informed Consent

The investigator is responsible for obtaining written informed consent from each individual participating in this study after adequate explanation of the aims, methods, objectives, and potential hazards of the study and before undertaking any study-related procedures. The

investigator must use the most current IRB- or IEC-approved consent form for documenting written informed consent. Each informed consent (or assent as applicable) will be appropriately signed and dated by the subject or the subject's legally authorized representative and the person conducting the consent discussion, and also by an impartial witness if required by IRB or IEC or local requirements. CCI

